## 2 Summary

#### 2.1 Background

Chronic atrophic gastritis is characterised by gastric mucosal atrophy and achlorhydria. Achlorhydria stimulates hyperplasia of gastric G-cells, which results in hypergastrinaemia. Hypergastrinaemia causes ECL-cell hyperplasia which leads to growth of gastric tumours (type I carcinoids) in about 5% of patients. About 80% of all gastric carcinoids are type I. Gastric carcinoids are rare; the prevalence is <1 per 10,000 population. Although most type I gastric carcinoids are benign, they all have the potential to become malignant and metastasise. Gastric surgery is the usual treatment for troublesome carcinoids.

There is much evidence that type I carcinoids are gastrin dependent. Therefore, YF476 – a potent, orally active, highly selective, competitive antagonist of gastrin receptors – might obviate the need for surgical removal of gastric carcinoids. Indeed, the European Commission and the USA Food and Drug Administration (FDA) have designated YF476 an Orphan Medicinal Product for treatment of gastric carcinoids.

#### 2.2 Trial medication

YF476 (50 mg: 2 x 25 mg capsules) by mouth *once* daily for 12 weeks. Taken with breakfast except on clinic visit days when patients will fast overnight and take YF476 after completion of assessments.

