There was no evidence of an effect of YF476 on QT interval. However, until we have more experience of YF476, patients with prolonged QT interval should be excluded from clinical trials of YF476 (Shah 2002).

YF476 was measured by the method of Redrup *et al* (2002). In early studies (before 2001), YF476 had linear pharmacokinetics, and consistent bioavailability. Absorption was rapid, and the terminal elimination half-life was about 6 h. AUC0-24 after 100 mg, the largest dose studied, was about 650 ng.h/mL, which is about a 5 to 60-fold safety margin in terms of AUC0-24 at NOAEL in the 13-week toxicology studies. Steady state was reached by Day 3, and there was no accumulation by Day 7. Only 1–2% was excreted unchanged in the urine.

However, in two subsequent studies (T-001 and T-009), for which we used a different formulation, plasma concentrations of YF476 were only about 10–15% of those achieved in the early studies. Despite the low bioavailability, YF476 showed good pharmacodynamic effects in study T-001 (effects of rabeprazole 40 mg and YF476 100 mg, alone and in combination for 6 weeks, on gastric function). In that study, gastric function was assessed by: 24-h ambulatory gastric pH; pentagastrin-stimulated gastric pH, volume and H+ output; 24-h serum gastrin profile; and 24-h plasma CgA profile (CgA is a biomarker for ECL-cell activity).

On Day 1 or 2, YF476 and rabeprazole by themselves gave similar results. They both:

- inhibited pentagastrin-induced increase in volume of gastric aspirate and H+ secretion;
- increased 24-h ambulatory gastric pH; and
- increased serum gastrin (a biomarker for gastric acid production), but did not affect plasma CgA (a biomarker for ECL-cell activity).

At 6 weeks, YF476:

- was as effective as rabeprazole in reducing gastric acid volume and H+ secretion;
- was as effective as rabeprazole in increasing serum gastrin, a biomarker for gastric acid production;
- did not increase plasma CgA, whereas rabeprazole increased it substantially;
- abolished the rabeprazole -induced increase in CgA; and
- augmented gastric acid suppression by rabeprazole without affecting the increase in gastric pH by rabeprazole.

The combination was more effective than either rabeprazole or YF476 alone in suppressing gastric acid production. Furthermore, the combination did not lose its effect on gastric pH after 6 weeks' dosing. On the contrary, the effect increased.

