#### 10.4 Withdrawal of subjects from the trial

Subjects are free to withdraw from the trial at any time without giving reasons. Furthermore, the investigator may withdraw a subject for medical reasons such as intolerance to trial medication, intercurrent illness, need for medication which is contraindicated, lack of efficacy of trial medication, or withdrawal of consent. The investigator will assess reasons for withdrawal as far as possible and will fully record the circumstances and medical details.

Subjects will be informed before they agree to take part in the trial that, if they withdraw:

- the investigator will stop collecting information about them; and
- they can ask the investigator to destroy any identifiable samples taken from them.

The investigator will ask withdrawn subjects to return unused trial medication, and to consent to a follow-up examination, to check that they have come to no harm as a result of taking part in the trial. Provided that subjects agree, they will undergo, at withdrawal from the trial, the standard medical examination and laboratory tests which they would have undergone had they completed the treatment regimen. The investigator will record in the CRF the results of the follow up examination of withdrawn subjects, if they give their consent for that.

For the extended treatment period, the following criteria apply:

Patients will be withdrawn from the study if they:

- have ALT or AST values >3 times the upper limit of normal;
- are found to have a prolonged QTc value (QTc ≥ 500 ms or QT prolongation with an increase of QTc > 60 ms compared to baseline);
- show any evidence of suspected drug-drug interaction; or
- experience an SAE or SUSAR which can reasonably be attributed to YF476.

If one of the criteria above is met in 2 or more subjects, dosing will be stopped in all subjects.

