### 12.2 Safety and tolerability

Vital signs, results of physical examinations, any adverse events (see section 16), laboratory safety variables (see section 14), and ECG variables. Evidence of QTc prolongation will be sought.

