# 14.3 Visit 3: 3 weeks after starting YF476

The investigator will:

- check that the patient has fasted;
- collect the diary card, and issue a new one;
- check the diary card for compliance with treatment, and for adverse events and concomitant medication;
- collect YF476 container and assess compliance;
- record a 12-lead ECG, and blood pressure and heart rate;
- collect blood and urine for safety tests, including a pregnancy test for women of child-bearing potential;
- collect blood for assay of fasting levels of gastrin, CgA, YF476 (trough), and serum for storage;
- after taking the fasting blood sample, give the patient their dose of YF476, wait 1 h, and then collect blood for assay of peak concentration of YF476;
- issue a second container of YF476 capsules (25 mg); 2 capsules to be taken with breakfast as before; and
- remind the patient to fast before their gastroscopy on Visit 4.

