# 14.4 Visit 4: 6 weeks after starting YF476

The investigator will:

- check that the patient has fasted;
- collect the diary card, and issue a new one;
- check the diary card for compliance with treatment, and for adverse events and concomitant medication;
- collect YF476 container and assess compliance;
- do a medical examination, including blood pressure and heart rate measurements, and 12-lead ECG;

- collect blood and urine for safety tests, including a pregnancy test for women of child-bearing potential.
- collect blood for assay of fasting levels of gastrin, CgA, YF476 (trough), and serum for storage;
- do a gastroscopy and take gastric biopsies, and proceed as follows:
  - if on visual inspection the gastric carcinoids have regressed completely: stop YF476, omit Visits 5 and 6, and proceed to Visit 7, providing all safety assessments prove satisfactory; or
  - if on visual inspection gastric carcinoids are still present: continue 50 mg YF476 *once* daily or consider increasing the dose to 75 or 100 mg *once* daily, issue a third container of YF476 capsules (25 mg); issue a new diary card;
  - after collecting the fasting blood sample and doing the gastroscopy, give the patient their dose of YF476, wait 1 h, and then collect blood for assay of peak YF476 concentration; and
  - instruct the patient about Visit 5.

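### Read as written, the only on-treatment ECG falls before the visit-day dose, at roughly 1–7% of peak YF476 concentration, and no ECG is scheduled near the 1 h peak sample

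*Protocol*

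**What the plan says.** **Order of events on visit days.** The summary of trial medication (Protocol 2.2) describes the dose as "Taken with breakfast except on clinic visit days when patients will fast overnight and take YF476 after completion of assessments". At Visit 3 (14.3) the investigator is to "record a 12-lead ECG, and blood pressure and heart rate". The blood and urine collections come next in the list, and then: "after taking the fasting blood sample, give the patient their dose of YF476, wait 1 h, and then collect blood for assay of peak" concentration. Visits 5, 9 and 11 (14.5, 14.9, 14.11) follow the same order. At Visit 4 (14.4), and likewise at Visit 6 (14.6), the instruction is to "do a medical examination, including blood pressure and heart rate measurements, and 12-lead ECG". It is listed ahead of blood sampling, gastroscopy and dose. Visit 10 (14.10) repeats the Visit 9 procedures and adds gastroscopy.

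**What is timed and what is not.** Footnote 7 to the flow chart in 6.2 keeps the patient for 1 h after dosing, for the peak blood sample. Footnote 2 in 6.3 times only the YF476 assay around the dose. The ECG method in 14.14 fixes posture, rest, paper speed and calibration, but not time from dose.

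**What the ECGs are for.** Section 12.2 says: "Evidence of QTc prolongation will be sought". Section 10.4 withdraws patients in extended treatment who "are found to have a prolonged QTc value", and stops dosing in all subjects if one of its criteria is met in two or more.

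**The concern.** The protocol treats peak concentration as the exposure that matters for QT: the hERG safety cover in 7.8.4 is expressed against the highest Cmax seen in a human subject. Yet the ECGs meant to detect QTc prolongation are placed, on the natural reading, about 24 h after the previous dose, when concentration is near its daily minimum. The patient then takes the dose and waits an hour in the clinic, but only blood is drawn.

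If YF476 had a QTc effect that rose and fell with concentration, this schedule would tend to miss it. The extension criterion in 10.4 would be tested when it is least likely to be met, and an unremarkable set of ECGs would say little about the hours around peak. The trial also doses for up to 12 weeks and then up to 52 weeks more. The longest completed study in 7.8.5, at 6 weeks, used a formulation that gave only about 10–15% of the earlier plasma concentrations.

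**Working it through.** The protocol gives no trough-to-peak ratio, so it has to be derived.

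**Inputs**
- Terminal half-life: "the terminal elimination half-life was about 6 h" (7.8.5, studies before 2001).
- Current formulation, 100 mg single dose: mean Cmax 265.3 ng/mL, mean AUC0–24 527 ng.h/mL. At 400 mg: 704.3 ng/mL and 1557 ng.h/mL (7.8.5, study T-011).
- Peak sample 1 h after dose (14.3 and the other visits). Once-daily dosing, so the pre-dose ECG is about 24 h after the previous dose.
- Assumption: 1 h is the peak. This is the protocol's label; no time to peak is given.

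**The protocol's own figure.** hERG cover: 4 × Cmax with 84% bound gives 4 / (1 − 0.84) = 25. The stated 25-fold cover reproduces, and it is a statement about Cmax.

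**Estimate 1: single-exponential decline from the 1 h sample.** The interval is 24 − 1 = 23 h.
- Half-life 6 h: 2^(−23/6) = 0.070, about 7% of peak.
- Assumed range 5 to 8 h: 2^(−23/5) = 0.041 and 2^(−23/8) = 0.136, so 4% to 14%.

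**Is that too high?** With k = ln 2 / 6 = 0.1155 per h, a 6 h decline starting at 265.3 ng/mL would give AUC0–24 = (265.3 / 0.1155) × (1 − 2^(−24/6)) = about 2153 ng.h/mL. The stated AUC is 527, about a quarter of that. The ratio AUC/Cmax is 527 / 265.3 = 2.0 h. The early fall must be much steeper than a 6 h half-life, so Estimate 1 overstates the trough.

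**Estimate 2: assign the whole AUC to the terminal phase.** C24 ≤ AUC × k × e^(−24k) / (1 − e^(−24k)).
- 100 mg: 527 × 0.1155 × 0.0625 / 0.9375 = 4.06 ng/mL; 4.06 / 265.3 = 1.5% of Cmax.
- 400 mg: 11.99 ng/mL; 11.99 / 704.3 = 1.7%.
- Assumed half-life 5 to 8 h, 100 mg: 1.0% to 2.5%.

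**Result**

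| Half-life | Estimate 1 (23 h) | Estimate 2 (100 mg) |
|---|---|---|
| 5 h | 4.1% | 1.0% |
| 6 h (stated) | 7.0% | 1.5% |
| 8 h | 13.6% | 2.5% |

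At the stated half-life the ECG is taken at roughly 1–7% of peak. Estimate 2 uses more of the protocol's data and is the more credible. Both rest on means in healthy subjects, and the half-life comes from studies before the current formulation.

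**The case against.** **The pre-dose timing is inferred.** A reader might take the protocol to state that ECGs are pre-dose and that QTc is never read near peak. It does not. Footnote 7 in 6.2, the most specific text, names the trough, gastrin and CgA samples and the gastroscopy as things to finish before dosing; the ECG is not among them. Section 2.2 cannot be literally exact either, since the 1 h sample is itself an assessment after the dose. An investigator could record the ECG during the wait without breaching a visit list. This stands, and the claim is limited accordingly. But nothing asks for such an ECG, and 2.2 and the list order point the other way.

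**The background sections promise no QT study.** A reader might infer from 7.8.5 and 7.9 that this trial undertakes to characterise QT. Those passages only justify excluding patients with a prolonged interval, which 10.3 does.

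**Prior evidence is reassuring.** Section 7.8.5 reports no evidence of a QT effect in nine completed studies, including single 400 mg doses with a mean Cmax 704.3 / 265.3 = 2.7 times that at 100 mg, the highest dose allowed here. Section 7.8.4 reports the hERG cover and no QTc effect in dogs. Appendix 1 excludes patients who need macrolides or azoles, and 20.1 permits extra safety tests. This lowers the likelihood of an effect; it does not supply a near-peak reading in these patients.

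**The trial is small.** With up to 10 patients, no control and one ECG per visit, no schedule would support a firm QTc conclusion, and the protocol claims none. That also stands.

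**Conclusion.** The concern holds in a limited form. Taken together, Section 2.2 and the visit lists put the only on-treatment ECG before the visit-day dose, and no section schedules one near the 1 h sample. At the stated half-life of about 6 h, and with 1 h taken as peak, that is roughly 1–7% of peak concentration. Over assumed half-lives of 5 to 8 h the two estimates span 1% to 14%, and the direction does not change. The aim in 12.2 and the criterion in 10.4 are therefore applied when a concentration-related effect is least visible.

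Three stronger conclusions do not follow. The documents give no sign that YF476 prolongs QTc. The primary objective is unaffected. And better timing would improve the chance of seeing a large effect without establishing QTc safety.

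One plain inconsistency sits alongside. Section 6.3 includes an ECG in the Visit 12 check, while 14.12 has Visit 12 repeat Visit 8, whose list in 14.8 contains none.

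**What to change.** 1. **Visits 3, 5, 9 and 11 (14.3, 14.5, 14.9, 14.11):** record the existing 12-lead ECG at the 1 h post-dose time, next to the peak sample. The 10 min supine rest required by 14.14 fits inside the wait.
2. **Visits 4, 6 and 10 (14.4, 14.6, 14.10):** leave the ECG before sedation and dose, and say so. Moving it is unsound here: midazolam may confound the reading, and at Visits 4 and 10 a complete responder stops YF476 subject to satisfactory safety assessments, so there may be no post-dose period. Because 14.10 repeats Visit 9, it needs its own statement of ECG time.
3. **Section 2.2:** amend it to match, and give the ECG time in the notes to 6.2 and 6.3.
4. **Summary:** present QTc change from the Visit 1 ECG alongside the measured peak concentration for Visits 3, 5, 9 and 11, separately from the pre-dose ECGs.
5. **Visit 12:** reconcile 6.3, 14.8 and 14.12 on whether an ECG is done.

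The thresholds in 10.4 are not in question here.

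**Cost.** No extra visit or procedure; the same ECG is taken later in the visit. The price is no pre-dose ECG at those four visits. The visit-day dose is also taken fasted, and 7.9 says food raises bioavailability, so the 1 h reading may still understate the usual at-home peak.

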#### 2.3 Objectives

The primary objective is:

• to assess if YF476 is an effective medical treatment for type I gastric carcinoids.

The secondary objectives are:

- to assess the tolerability and safety of YF476; and
- to assess the effect of YF476 on plasma concentration and transcript profiles of biomarkers such as chromogranin A (CgA).

#### 2.4 Type of trial

Single centre, open-label, pilot, phase 2, out-patient trial.

#### 2.5 Trial population

**Total** up to 10 patients.

#### Inclusion criteria

- 1. Patients known to have gastric carcinoids associated with chronic atrophic gastritis and hypergastrinaemia and who attend the out-patient clinic of the investigators.
- 2. Men; post-menopausal women; pre-menopausal women who have been sterilised by tubal ligation, hysterectomy or bilateral oophorectomy; or pre-menopausal women using one of the allowed methods of contraception: condom and spermicide or intra-uterine device.
- 3. Adults  $\geq 18$  years.
- 4. Good general health.
- 5. Able to give fully-informed, written consent.

#### **Exclusion criteria**

- 1. Women who are pregnant, lactating or using a steroid contraceptive.
- 2. History of gastric surgery, apart from surgery for gastric carcinoids.
- 3. Evidence of Zollinger-Ellison syndrome.
- 4. Prolonged QTc interval (> 450 msec).
- 5. Certain medicines and herbal remedies (see Appendix 1) taken during the 7 days before Visit 1.
- 6. Previous treatment with somatostatin analogues.
- 7. Participation in other clinical trials of unlicensed medicines within the previous 3 months.

#### 2.6 Trial design

Patients will attend the clinic up to 12 times. The time that patients take to complete the trial will depend on their response to YF476.

At Visit 1, patients will be screened (excluding gastroscopy) for eligibility.

At **Visit 2**, patients will undergo gastroscopy and gastric biopsies. If they meet all the inclusion/exclusion criteria, they will start treatment with 50 mg YF476 by mouth *once* daily at home on the next day. Each subject will be given a unique number at the start of treatment.

They will complete a diary card daily throughout the treatment period.

**Visit 3** will be 3 weeks after starting YF476, to assess tolerability, safety and blood levels of gastrin, CgA and YF476.

**Visit 4** will be 6 weeks after starting YF476, to assess tolerability and safety, to repeat the gastroscopy and gastric biopsies, and to take blood samples to assess levels of gastrin, CgA and YF476. If the gastric carcinoids have regressed completely on visual inspection, YF476 will be stopped, Visits 5 and 6 will be

omitted, and the patient will proceed to Visit 7. If the gastric carcinoids are still present, YF476 will be continued, but the dose may be increased to 75 or 100 mg *once* daily, at the discretion of the investigator. If a satisfactory response is seen with 50 mg YF476 *once* daily after 6 weeks for the first few patients, subsequent patients may be started on 25 mg YF476 *once* daily.

**Visit 5** will be 9 weeks after starting YF476, to assess tolerability, safety and blood levels of gastrin, CgA and YF476.

**Visit 6** will be 12 weeks after starting YF476, to assess tolerability and safety, to repeat the gastroscopy and gastric biopsies, and to take blood samples to assess levels of gastrin, CgA and YF476. If the carcinoids have not regressed, the patient will leave the trial. If the carcinoids have regressed, the patient will proceed to Visit 7.

**Visit 7** will be a follow-up visit, 12 weeks after the end of treatment with YF476, only for patients who respond to YF476. The gastroscopy and blood sampling (for gastrin and CgA) will be repeated.

#### **Extended treatment**

Some patients will be eligible for extended treatment with YF476, as described below. To be eligible for further treatment, the patient must have benefitted from 12 weeks' treatment, and have tolerated YF476 well, and must give fully informed written consent.

**Visit 8** will be to inform the patient about the extended dosing period and prescribe YF476 capsules. If the investigator thinks that a new baseline gastroscopy and blood sampling (for safety, gastrin and CgA) is necessary, this will be carried out.

**Visit 9** will be 12 weeks after starting extended treatment with YF476, to assess tolerability, safety and blood levels of gastrin, CgA and YF476.

**Visit 10** will be 24 weeks after starting extended treatment with YF476, to assess tolerability and safety, to repeat the gastroscopy and gastric biopsies, and to take blood samples to assess blood levels of gastrin, CgA and YF476.

**Visit 11** will be 36 weeks after starting extended treatment with YF476, to assess tolerability, safety and blood levels of gastrin, CgA and YF476.

**Visit 12** will be 52 weeks after starting extended treatment with YF476, to assess tolerability and safety, to repeat the gastroscopy and gastric biopsies, and to take blood samples to assess levels of gastrin, CgA and YF476.

A formal follow-up visit will be omitted, as the patients are closely followed by the investigator as part of their standard healthcare.

The end of the trial will be the last visit by the last subject.

#### 2.7 Methods

- Gastroscopy with photographs and video of carcinoids, and biopsies of antrum, corpus and carcinoids;
- Blood samples for assay of gastrin, CgA, and YF476, and serum for storage;
- Diary card: adverse events, concomitant medication and compliance; and
- Tolerability and safety assessments.

#### 2.8 Variables

- Visual assessment of the number, size and distribution of gastric carcinoids;
- Histology and real-time PCR of biopsies: for ECL-cell markers and biomarkers (such as CgA);
- Fasting serum gastrin and plasma CgA concentrations;
- Trough and peak serum YF476 concentrations; and
- Medical examination; ECG; vital signs; adverse events; and safety tests of blood and urine.

# 4 List of abbreviations

ABPI	Association of the British Pharmaceutical Industry
ALT	alanine aminotransferase
AST	aspartate aminotransferase
AUC	area under the curve
BP	blood pressure
°C	degrees Celsius
CAG	6
CAG CCK-B	chronic atrophic gastritis cholecystokinin B
	chromogranin A
CgA	centimetre
cm CRF	
	case report form
CYP	cytochrome P450 enzyme
D	decreased by more than predetermined amount from screening value,
ECC	or Day, according to context
ECG	electrocardiogram
ECL cell	enterochromaffin-like cell
EDTA	ethylenediamine tetraacetic acid
FDA	Food and Drug Administration
G	gauge or G force, according to context
g CCD	gram
GCP	Good Clinical Practice
GP	General Practitioner
gamma-GT	gamma glutamyl transpeptidase
GMP	Good Manufacturing Practice
GORD	gastro-oesophageal reflux disease
GRA	gastrin receptor antagonist
GT	glutamyl transpeptidase
H	higher than normal range
HDC	histidine decarboxylase
H2RA	histamine H 2 -receptor antagonist
h UTh	hour haamaalahin
Hb Handoni	haemoglobin Usliggh actor mylani
H. pylori	Helicobacter pylori
hERG	human ether-à-go-go related gene
HMR	Hammersmith Medicines Research
I	increased by more than predetermined amount from screening value
ICH	International Conference on Harmonisation of
	Technical Requirements for Registration of Pharmaceuticals for
10	Human Use
$IC_{50}$	concentration of drug causing 50% inhibition of a response
IMP	investigational medicinal product
ISO	International Standards Organization
kg	kilogram
L	lower than normal range or litre, according to context
m MEN 1	metre
MEN 1	multiple endocrine neoplasia-1 gene
MIA(IMP)	Manufacturer's Authorisation for Investigational Medicinal Products

MCV MedDRA MHRA mg min mL mm mm Hg MMP-7 mV ng NOAEL NRES NSAID PC PCR PCR PCR PCR PCR PFI QA QTC REC SAS SST sec SUSAR uPA VMAT WBC ZES	mean corpuscular volume Medical Dictionary for Regulatory Activities Medicines and Healthcare products Regulatory Agency milligram minute or minimum, according to context millimetre millimetre millimetres of mercury matrix metalloproteinase-7 millivolts nanogram no-observable-adverse-effect level National Research Ethics Service non-steroidal anti-inflammatory drug personal computer polymerase chain reaction the negative logarithm to base 10 of the hydrogen ion concentration pancreastatin proton pump inhibitor Quality Assurance interval of the ECG corrected for heart rate Research Ethics Committee statistical analysis software somatostatin second suspected unexpected serious adverse reaction urokinase-type plasminogen activator vesicular monoamine transporter white blood cells Zollinger-Ellison syndrome
	-
μg	microgram
μmol	micromole

